### **9.1.6. Death**

All deaths occurring any time from the time of informed consent to study conclusion will be summarized by reason and presented in a table. A supportive listing will be generated to provide patient-specific details including the reason for death for all patients in the ITT Set.

## **9.2. Serum Chemistry**

Blood samples will be collected for clinical laboratory testing at screening for all patients. Blood samples will additionally be collected for patients who discontinue topiramate and switch to BOTOX prior to their first administration of BOTOX.

The following serum chemistry laboratory tests will be included: blood urea nitrogen (BUN) (mg/dL), calcium (mg/dL), creatinine (mg/dL), sodium (mEq/mL), potassium (mEq/mL), chloride (mEq/mL), carbon dioxide (mEq/mL), and alkaline phosphatase (U/L). All chemistry data will be presented in a by-patient listing.

Laboratory assessments will be performed by a central laboratory. All summaries will be based on the units provided by the central laboratory; no conversion will be done.

## **9.3. Vital Sign Measurements**

Vital signs will be measured at screening, Day 1, and each subsequent office visit.

Systolic and diastolic blood pressure and pulse rate over 30 seconds should be taken after patients have been at rest (seated) for at least 2 minutes. Blood pressure should be recorded in mmHg. Pulse rate should be measured in beats per minutes. Oral, axillary, or tympanic body temperature should be taken. The same route should be used throughout the study. If oral temperature is taken, the patient should not have any oral intake for at least 5 minutes prior to the measurement. Temperature as Fahrenheit (°F) or Celsius (°C) should be specified on the source document and the eCRF.

Summary tables will be presented for vital sign data by treatment group for patients in the Safety Set. Observed results at each visit will be presented.

All vital sign data will be presented in a by-patient listing.

#### **9.4. Physical Examination**

At screening and study exit, the investigator will examine the patient for any detectable abnormalities of the following body systems: general appearance; neck (including thyroid); head, eyes, ears, nose, and throat; lungs; heart/cardiovascular; abdomen; neurologic; extremities; back; musculoskeletal; lymphatic; skin; and other. The neurologic examination should be conducted to detect the presence of any significant sensory/motor abnormalities.

Height and weight should be measured at screening, Day 1, and each subsequent office visit using the same scale and ruler for all patients at a given investigator site when possible.

A table will summarize physical examination results by treatment group and overall for the Safety Set. Each visit captures the status of a body system and any finding associated with the body system as normal, abnormal, or not done. The summary will include the number and percentage of patients with each physical examination outcome for the following body systems: skin; head, eyes, ears, nose, and throat (respiratory; cardiovascular; gastrointestinal; endocrine/metabolic; genitourinary; neurological; blood/lymphatic; musculoskeletal; and other. Patients will be counted in the arm in which they were treated. Denominators for percentages will be the total number of patients treated in each arm.

Physical examination results for all patients will be presented in a listing.

#### **9.5. Pregnancy Test**

Urine pregnancy testing will be conducted at screening, on day 1, and each subsequent office visit to confirm continued non-pregnant status prior to study drug administration or study completion.

A listing will be presented for pregnancy test status.

## **9.6. Urine Drugs of Abuse**

Illicit drug urine testing will be conducted at screening and day 1, prior to study treatment administration, and will be performed at the investigator site.

A listing will be presented for urine drugs of abuse at screening.

## **9.7. Columbia-Suicide Severity Rating Scale (C-SSRS)**

The C-SSRS will be conducted at the screening visit and each subsequent office visit. At screening, patients will be asked about the 12 months prior to the screening visit along with a separate assessment for lifetime prior to the screening visit. For visits after the screening visit, the assessment will be for the time period since the previous visit. The assessments will be summarized for each treatment group using the Safety Set.

Among the questions for each assessment time period (lifetime, prior 12 months, since previous visit) are a set of 10 questions intended to elicit a yes or no response from the patient (as deduced by the investigator site's interview of the patient) and a question (post-screening only) regarding completed suicide. Among those questions are 5 regarding suicidal ideation, arranged in order of increasing severity (1= wish to be dead, 2= non-specific suicidal thoughts, 3= method without intent to act, 4= some intent but without plan and 5= intent and plan). Also included are 6 questions in the suicidal behavior section of the C-SSRS (non-suicidal self-injurious behavior, preparatory behavior, aborted attempt, interrupted attempt, actual attempt, and completed suicide).

C-SSRS data will be summarized separately for the following sets of responses: (1) year prior to screening, (2) baseline as reported under "since screening" at the randomization visit and (3) by visit reported as "since last visit." Overall ideation and behavior responses for the treatment period will be done by taking the most severe response (eg, a yes response at any time point for a specific ideation or behavior question).

Counts and percentage of patients with each answer on the questionnaire will be provided. Summary statistics will include the count and percentage of patients for each of the 11 ideation and behavior categories separately and also overall for any ideation, for any behavior and for any ideation or behavior. Denominators for percentages will be the total number of patients treated in each arm.

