## 9. Safety Analyses

All analyses of safety will be conducted using the Safety Set. All patients will be summarized according to the treatment they actually received, but the subgroup of topiramate patients who initially received topiramate and then switched to BOTOX will be summarized as follows:

- All safety assessments occurring prior to the date of the first dose of BOTOX will be summarized for the topiramate treatment arm.
- All safety assessments except AEs occurring on or after the date of the first dose of BOTOX will be summarized separately for the topiramate + BOTOX subgroup. For all AEs, the total number of patients (N) in each treatment arm will represent the number of patients that received that treatment. A patient may be counted in both treatment arms. The overall total will be the number of patients that received any treatment. The topiramate + BOTOX treatment arm will be a subset of the BOTOX treatment arm and will include patients that received both treatments. Denominators for percentages will be the total number of patients in each treatment arm or overall. Treatment-emergent AEs (TEAEs) include all AEs that start on or after the first dose of study medication up to the final visit, or are present prior to the first dose but increase in severity after the first dose of study medication up to the final visit. For patients who switch from topiramate to BOTOX, TEAEs starting on or after the date of the first BOTOX injection will be counted in the treatment arm that they are related to, as determined by a physician. If the TEAE is related to both treatments or if the relationship is unknown, it will be counted in both treatment arms but only once in the total. The topiramate + BOTOX subset will summarize all TEAEs that occurred after a patient has switched from topiramate to BOTOX.

Statistical hypothesis testing will not be performed on any safety results

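### The planned C-SSRS tables do not separate new or worsened ideation from recurrence in the same patient, and the switch-visit interview can fall in the wrong column

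*SAP*

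**What the plan says.** SAP 9.7 collects two look-backs before treatment: "At screening, patients will be asked about the 12 months prior to the screening visit along with a separate assessment for lifetime prior". A further since-screening response is taken at randomisation. After screening, "For visits after the screening visit, the assessment will be for the time period since the previous visit".

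The tables are then split by period: "C-SSRS data will be summarized separately for the following sets of responses: (1) year prior to screening, (2) baseline as reported" since screening, and (3) by visit. Lifetime answers are not among the three listed sets, although a general sentence earlier in the section says the assessments will be summarised by treatment group.

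For the treatment period, "Overall ideation and behavior responses for the treatment period will be done by taking the most severe response", which the SAP illustrates as "a yes response at any time point for a specific ideation or behavior question". The denominator is unconditional: "Denominators for percentages will be the total number of patients treated in each arm".

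SAP 9 sets the frame. No safety result is tested: "Statistical hypothesis testing will not be performed on any safety results". For patients who move from topiramate to BOTOX, non-AE safety assessments dated before the first BOTOX dose count under topiramate. Those dated on that day or later go to a separate topiramate + BOTOX subgroup.

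**The concern.** A yes on treatment can mean two things: ideation that is new or worse than before the first dose, or ideation the patient already had. Only the first bears directly on a drug effect, and the planned count adds the two together. The prior-year and baseline tables show how common earlier ideation was in each arm, but not whether the patients positive before treatment are the ones positive afterwards. SAP 9.7 names no shift table, no new-or-worsened definition and no denominator of patients negative beforehand.

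The same SAP is stricter elsewhere. Under SAP 9.1 an adverse event already present before the first dose is treatment-emergent only if its severity increases afterwards. The C-SSRS ideation items are ordered by severity, so a parallel rule is available but is not used.

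For switchers there is also a dating problem. An interview that describes time before BOTOX may be tabulated as if it described time after it. Comparing the safety of the two treatments is a stated objective, so a reader will look at these columns.

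**Working it through.** **The plan's own figure.** The only design number needed is the arm size. Protocol 7.5 and SAP 4.1 give 200 per group for 28% against 44%, two-sided α = 0.05, 90% power, continuity-corrected chi-squared. With mean rate 0.36:

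- Uncorrected: n′ = [1.960·√(2·0.36·0.64) + 1.282·√(0.28·0.72 + 0.44·0.56)]² / 0.16² = 187.05, rounded up to 188.
- Corrected: n = (n′/4)·[1 + √(1 + 4/(n′·0.16))]² = 199.4, rounded up to 200. The stated figure reproduces.

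Neither document gives a C-SSRS rate. Every rate below is an assumption, applied to 200 per arm.

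**Dilution.** Let h be the share with pre-treatment ideation, q the chance that such a patient says yes again on treatment (equal in both arms), and r the new-onset rate among the rest. Then any-yes rate = h·q + (1 − h)·r. With q = 0.5 and r = 1% against 3%:

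| h | Any yes, lower arm | Any yes, higher arm | Ratio | Difference (points) | SE of difference (points) |
|---|---|---|---|---|---|
| 0% | 1.00% | 3.00% | 3.00 | 2.00 | 1.40 |
| 2% | 1.98% | 3.94% | 1.99 | 1.96 | 1.69 |
| 5% | 3.45% | 5.35% | 1.55 | 1.90 | 2.05 |
| 10% | 5.90% | 7.70% | 1.31 | 1.80 | 2.52 |

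At h = 5%, recurrences make up 0.025/0.0345 = 72% of positives in the lower arm and 0.025/0.0535 = 47% in the higher arm. With r = 2% against 5%, the ratio of 2.5 becomes 1.99, 1.65 and 1.40 at the same three values of h. The difference barely moves. The ratio shrinks and the noise grows.

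**Chance imbalance with no drug effect.** Take h = 10%, q = 60%, r = 2% in both arms.

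- Any yes = 0.10·0.60 + 0.90·0.02 = 7.8%, of which 1.8 points (23%) are new.
- A 1-SE arm difference in earlier ideation is √(2·0.10·0.90/200) = 3.0 points. Multiplied by (0.60 − 0.02), it carries 1.74 points into the on-treatment comparison.
- Like for like, the full 1-SE noise in the any-yes difference is √(2·0.078·0.922/200) = 2.7 points. For a new-onset count it is √(2·0.018·0.982/200) = 1.3 points.
- Over h = 5% to 15% and q = 40% to 80%, the new share runs from 49% down to 12%, and the carried-over difference from 0.8 to 2.8 points.

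**The switch visit.** This step needs no assumed rate.

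1. A patient who stops topiramate gets the first BOTOX treatment at the next scheduled office visit (protocol 5.4.2.2 and 8.8).
2. The C-SSRS is done at every office visit (protocol 6.5) and asks about the time since the last one (SAP 9.7). At the switch visit it therefore covers time before BOTOX, some or all of it on topiramate.
3. SAP 9 allocates by date. An interview dated on the day of the first BOTOX dose falls in the topiramate + BOTOX subgroup.
4. The scheduled post-dose office visits start at week 12. A patient who switches at week 12 would then add no scheduled on-treatment C-SSRS to the topiramate column, while still counting in its denominator.
5. For adverse events after the switch, SAP 9 and 9.1 ask a physician to attribute the event. The C-SSRS has no equivalent.

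**The case against.** The strongest reply is that nothing here is an error. SAP 9.7 does not contradict itself, no test or alpha depends on it, and prior-year and baseline responses are tabulated by arm, so a chance imbalance would be visible beside the on-treatment counts. History is not carried forward automatically either: an on-treatment yes must refer to the interval since the last visit. All of this stands, and it limits the point to the missing within-patient link.

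The withdrawal rule is a second limit. Under protocol 8.9, a yes to ideation item 4 or 5, or to any behaviour question, ends study treatment and participation. Repeated positives, and ideation persisting through a switch, therefore mainly concern items 1 to 3. Discontinuations due to the C-SSRS are also counted by the treatment being received at the time (SAP 5).

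Third, the rates used above have no anchor in the documents. Several eligibility criteria are blacked out, and a psychiatric or C-SSRS criterion among them could make earlier ideation rarer than assumed. A new-onset count would also be noisy, as the 1.3 points show.

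A reader might infer that the any-yes count biases the comparison of BOTOX with topiramate. The documents do not support that: allocation is randomised 1:1, so recurrence is balanced in expectation. A reader might also infer that switchers' earlier ideation is charged to the randomised BOTOX column. It is not, because SAP 9 keeps their non-AE assessments in a separate subgroup.

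What survives is that arm-level percentages cannot show who is new, and that allocation by date misplaces the switch-visit look-back.

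**Conclusion.** The point holds as a modest gap in a descriptive safety summary. No planned C-SSRS summary separates new or worsened ideation from recurrence in the same patient. Between randomised arms the consequence is dilution and added chance noise, mainly for ideation items 1 to 3. No efficacy result or formal inference is touched.

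Its size cannot be fixed from the documents. Under the assumed rates, a new-onset risk ratio of 3.0 appears as 1.99 to 1.31 when 2% to 10% of patients have earlier ideation and half of them report it again. The risk difference stays between 1.80 and 1.96 points, but its standard error rises from 1.40 to as much as 2.52 points.

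The switch-visit problem rests on a literal reading of SAP 9 and on the interview carrying the date of the first BOTOX dose. If the sponsor already intends to class that interview as pre-BOTOX, a sentence saying so settles it.

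**What to change.** Add three items to SAP 9.7:

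- A shift table of the worst pre-treatment category (prior 12 months and since screening, with lifetime shown as well) against the worst on-treatment category, for each treatment column.
- The number and percentage of patients whose on-treatment ideation or behaviour is new, or in a higher category than before treatment.
- A rule that the C-SSRS at the switch visit, which covers time before the first BOTOX dose, is counted under topiramate and forms part of the pre-BOTOX reference for the topiramate + BOTOX column. This follows the logic the SAP already applies at randomisation, where the since-screening response serves as baseline.

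No new data are needed. The cost is one extra table, and its cells will be small, so it should be read as description only.

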## **10. Interim Analysis**

There is no interim analysis planned for this study.

## 11. Deviation from Protocol-Specified Analyses

The subset of ITT and Per-protocol population analyses will not be performed since subjects who would be discontinued due to reasons specified and subjects with major protocol deviations, respectively, is expected to be few; hence difference on number of subjects in each of the two populations and the ITT population is minimal.

